Aim 2. To determine if CBD oil has any effect in decreasing the amount of postoperative opioids (commonly used drug) used by patients after undergoing ureteroscopy for urinary stone disease. We will test the hypothesis that patients randomized to CBD oil will have decreased usage of postoperative opioids given as a rescue

medication compared to those randomized to the control condition also given opioids as a rescue medication. We will analyze number of use, the cumulative and per day usage of analgesic opioid medication.

Background (Include relevant experience, gaps in current knowledge, preliminary data, etc.):

Ureteroscopy is one of the mainstays of the surgical management of upper urinary tract calculi. In most cases, a ureteral stent is left postoperatively which unfortunately can lead to significant morbidity and discomfort for the patient.¹ More than 80% of patients with a stent post-ureteroscopy report pain that interferes with their daily activities.¹ It is common for providers, and typical protocol at our institution, to prescribe opioids post-operatively for pain control.

In the past 15 years the number of opioid medication prescriptions in the United States has quadrupled. According to the CDC more than 47,600 people died from opioid overdoses in 2017, with one in three of those from prescription opioids.³ Currently, Arizona has one of the highest age-adjusted rates of drug overdose deaths in the country.³ Rates of death from overdose in Arizona was also shown to be increasing in recent years. Given the dramatic increase in opioid medication prescriptions in the United States, there has been a significant move towards finding alternative medications to manage patients' pain.

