Trial medication will be stored by the study pharmacy in a locked and labeled drawer for this particular study until they are dispensed to the patients. Records of allocation and dispensation will be kept by the pharmacy.

The dosage of trial medication will be 20 mg daily.

Patients will receive a prescription for an opioid per usual post-ureteroscopy protocol. For this study patients will receive a prescription for oxycodone 5 mg, 12 tabs. Instructions will consist of instructing the patient to take the medication as needed -1 tab per mouth every 6 hours as needed for pain, for a maximum of 3 days.

Common adverse reactions to CBD oil include somnolence, decreased appetite, and diarrhea. In addition, elevated liver function tests (LFTs) were noted in patients treated with a different CBD oil product, Epidiolex, which is FDA approved for pediatric seizures associated with Lennox-Gastaut syndrome For Epidiolex, the FDA recommends pre-treatment LFTs drawn. These should be repeated after 1 month and 3 months of treatment¹¹, which will be significantly outside out treatment window of 3 days.

Patients will be asked to refrain from drinking any alcohol or consuming marijuana-based products during the study period.

Identification and enrollment of patients

Patients will undergo standard consultation for treatment options for urinary stones. Patients electing to undergo ureteroscopy for upper tract urinary stone disease will be identified and considered for enrollment during preoperative counseling in the urology clinic. Those who satisfy the inclusion and exclusion criteria will then be approached for inclusion into the study. Background, significance, risks, benefits, and alternatives will be discussed in detail and all questions will be answered before signing the consent form. A copy of the research consent form with all of the above information will be given to the patients and the signed original consent form will be kept in the urology department as detailed in the Data Collection and Handling section.

Randomization and allocation

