Patients will be randomized to one of two groups – trial medication or placebo. Randomization schedule will be generated by the study statistician. Block randomization will be used to ensure temporal balance. Once patients have consented to being included in the study, they will be assigned a sequential study number, which will be passed onto the pharmacy study contact at the appropriate site to assign randomization allocation. They will then dispense encapsulated trial medication based on that allocation.

Blinding

This is designed to be a double blinded, placebo controlled trial in which neither the patient nor the clinical team is aware of the group allocation. The medications will be packaged inside a syringe. The medication will be dispensed to the patient with a label that describes both medications, strengths, and administration schedule. The clinical team will be blinded to the allocation and will only receive the dispensed drug from the pharmacy contact and then bring it to the discharging nurse in the recovery room for inclusion with other discharge material.

Preoperative and perioperative procedures

- Patient will undergo standard preoperative procedures including baseline blood work (CBC, BMP, and LFTs), imaging, and medical clearance as required.
- The procedure itself will be performed per standard practice of the surgeon, including choice of instruments, manner of fragmentation, and postoperative management of patient with regards to follow up appointments, stent placement and removal.

Postoperative procedures

- The study pharmacy will disguise the appropriate drug into an unlabeled generic container and dispense the prescription with appropriate instructions.
- In the recovery room, the patient will fill out a 100mm pain visual analog scale sheet which will be kept in the study drawer in the urology department.
- The patient will then be given a packet of materials for data collection along with the syringe with the blinded medication with full administration instructions and safety leaflet.
- The patient will fill out the data sheets for pain scale, trial, rescue and other medication usage, and adverse events on a daily basis for three days. The patient will also fill out the Ureteric Stent Symptoms Questionnaire (USSQ) on postoperative days 1 and 3.
- Patient will then mail the data sheets to the urology department using a provided stamped-addressed envelope or hand in the data sheets at their postoperative appointment.

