- The patient will be required to bring all unused trial medication to the postoperative appointment, which will then be returned to the pharmacy staff.

Rescue medication protocol

- Patients will be prescribed an opioid pain medication per the typical protocol of the operating surgeon (12 tabs of oxycodone 5 mg). This can be taken at the patient's discretion for increased pain.
- All usage of opioids will be recorded by the patient on the daily data sheet.

• Given that the presence of the stent itself can be a significant factor in the pain and discomfort for patients undergoing URS, we will also allow for patients to be prescribed oxybutynin, tamsulosin and/or phenazopyridine at the discretion of the clinical team. These two medications, along with tamsulosin (given to patients routinely following URS) are very commonly used to mitigate stent pain in post-URS patients. Use of all adjunct medications will be recorded by the patient on the daily data sheet.

Emergency situation procedures

Participants will be given a patient card, which will have the study title, investigational medication product details, participant identification number and contact details for clinical study team members for business and after hours. If a patient has pain which is not controlled despite use of trial and rescue medications, then patient will have the option to call into the surgeon's office (during business hours) or the after-hours call number, which is usually directed to the resident on call. The patient will give the trial information on the patient card to the resident returning the call. Treatment plan at that point will be developed by the resident in conjunction with on call staff as per usual protocol. This may include medications prescribed over the phone, scheduling office visits as well as emergency room visits.

Subject withdrawal

Participants will remain on the trial unless they choose to withdraw or they no longer meet the inclusion and exclusion criteria.

Outcome measures

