The primary outcome measure will be the pain score given by patients on the 100mm continuous visual analog scale (VAS). The VAS is an easy to use instrument for evaluating pain severity. It provides reproducible results that do not differ with age, gender or cause of pain. It is sensitive to treatment effects and data derived from it can be analyzed with standard parametric statistical techniques. Each day, patients will record their maximum and average pain scores. Surveys to record the pain scores and rescue drug (oxycodone) administration will be handed to the patient on day of surgery as well as emailed out via an external REDCap database. We will combine the results from each study and compare the primary outcome between the two groups (i.e. control group and CBD oil group) in two ways: 1. overall, and 2. on a per day basis. Secondary outcomes

- We will compare the number of use, the cumulative and per day usage of analgesic opioid medication between the two groups.
- Usage of other medications, either self-administered, or prescribed will be compared
- The rate of adverse clinical events defined as the rate of adverse drug reactions, rate of unscheduled phone calls, emergency room visits, hospital admissions, and clinic visits will be compared between the two groups. Collection of adverse events will be done by a combination of patient self-report on data sheets and data gathering from electronic medical record to search for evidence of phone calls, emergency room visits, hospital admissions, clinic visit notes.
- Comparison of ureteral stent symptom questionnaire (USSQ) scores on postoperative days 1 and 3.

Subject Information

Target accrual is the proposed total number of subjects to be included in this study at Mayo Clinic. A "Subject" may include medical records, images, or specimens generated at Mayo Clinic and/or received from external sources.

Target accrual: 90

Subject population (children, adults, groups): Adults treated at Mayo Clinic, Arizona for kidney stones with ureteroscopy.

Inclusion Criteria:

- Patients who are diagnosed with kidney or ureteral stones confirmed on imaging (CT of the abdomen and pelvis) and who elect for definitive treatment via ureteroscopy at two sites within a tertiary care institution
- Age 18-75
- Patients of either gender
- Patients of all ethnic backgrounds
- Capable of giving informed consent
- Capable and willing to fulfill the requirements of the study

Exclusion Criteria:

- History of chronic pain

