- Chronic use of opioid or other pain medication (>12 weeks)
- Known allergy to CBD oil or other cannabinoids
- Known or suspected pregnancy
- Inability to give informed consent or unable to meet requirements of the study for any reason
- Bilateral ureteroscopy
- Current marijuana, cannabidiol (CBD), or dronabinol use
- Liver disease/cirrhosis
- Current treatment of seizures with clobazam, valproate, or other antiepileptic medications

Biospecimens

Collection of blood samples. When multiple groups are involved copy and paste the appropriate section below for example repeat section b when drawing blood from children and adults with cancer.

a. From healthy, non-pregnant, adult subjects who weigh at least 110 pounds. For a minimal risk application, the amount of blood drawn from these subjects may not exceed 550ml in an 8 week period and collection may not occur more frequently than 2 times per week.

Volume per blood draw: __0___ml

Frequency of blood draw (e.g. single draw, time(s) per week, per year, etc.) _____0____

b. From other adults and children considering age, weight, and health of subject. For a minimal risk application, the amount of blood drawn from these subjects may not exceed the lesser of 50 ml or 3 ml per kg in an 8 week period, and collection may not occur more frequently than 2 times per week. Volume per blood draw: __0__ml

Frequency of blood draw (e.g. single draw, time(s) per week, per year, etc.) _____0____

Prospective collection of biological specimens other than blood: ______None_____

Review of medical records, images, specimens

Check all that apply (data includes medical records, images, specimens).

Only data that exists before the IRB submission date will be collected.

Date Range for Specimens and/or Review of Medical Records:

Examples: 01/01/1999 through 12/31/2015, or all records through mm/dd/yyyy.

Note: The Date Range must include the period for collection of baseline data, as well as follow-up data, if applicable.

The study involves data that exist at the time of IRB submission **and** data that will be generated after IRB submission. Include this activity in the Methods section. Examples

- The study plans to conduct a retrospective chart review and ask subjects to complete a questionnaire.
- The study plans to include subjects previously diagnosed with a specific disease and add newly diagnosed subjects in the future.

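### Preoperative opioid use of 12 weeks or less is not clearly excluded, not recorded at baseline, and not adjusted for in the Aim 2 opioid comparison

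*Combined protocol and SAP*

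**What the plan says.** **Eligibility.** The Exclusion Criteria bar "Chronic use of opioid or other pain medication (>12 weeks". They also bar "History of chronic pain", without a definition or a duration. Cannabinoids are handled differently: "Current marijuana, cannabidiol (CBD), or dronabinol use" is excluded with no minimum duration.

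**Conduct.** Under Study Design and Methods, "Patients will be asked to refrain from drinking any alcohol or consuming marijuana-based products during the study period". Opioids left over from an earlier prescription are not mentioned.

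**Outcome.** Aim 2 hypothesises that "patients randomized to CBD oil will have decreased usage of postoperative opioids given as a rescue", and adds: "We will analyze number of use, the cumulative and per day usage of analgesic opioid medication".

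**Recording.** Postoperative procedures set a three-day recording period: "The patient will fill out the data sheets for pain scale, trial, rescue and other medication usage, and adverse events on a daily basis for" that period. The Rescue medication protocol adds: "All usage of opioids will be recorded by the patient on the daily data sheet". Outcome measures describes surveys that capture the rescue drug, identified as oxycodone. It lists the use of other drugs, self-taken or prescribed, as a separate secondary outcome.

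**Baseline and analysis.** The preoperative procedures cover blood work, imaging and medical clearance. Randomisation is blocked, with no stratification factor named. The Data Analysis Plan compares opioid use by t-test or chi-square test. It fits a regression only if baseline imbalance appears, and it names no covariates.

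**The concern.** Aim 2 is about opioid taken as rescue after ureteroscopy. A patient with a symptomatic stone may already have been taking an opioid for some weeks and may have tablets at home. What that patient takes in the three days after surgery can partly reflect the earlier use rather than new postoperative pain.

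If such patients are enrolled and not identified, two things suffer. The opioid outcome becomes more variable, which costs precision in a trial of 45 per group. A difference, or the lack of one, also becomes harder to read as an effect on rescue use. Neither problem can be repaired reliably afterwards if preoperative use was not asked about before surgery.

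**Working it through.** **1. Can such patients enter?** The opioid criterion starts beyond 12 weeks. No other criterion names current or recent opioid use. The chronic-pain exclusion might remove some of these patients, but with no definition it cannot be relied on to remove all. Some can therefore enter; how many is unknown.

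**2. Would the analysis know who they are?** No section names preoperative opioid use as a study variable. The conditional regression cannot adjust for a variable that is not collected.

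**3. Which outcome would their own opioid enter?** The daily sheet lists rescue and other medication as separate items, and the surveys identify the rescue drug as oxycodone. That points towards separation. Against it, all opioid use is recorded, and the analysed outcome is opioid medication with no source specified. The text does not settle the question. Study oxycodone taken to meet a pre-existing need would count as rescue either way.

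**4. The plan's own figure.** The Power Statement gives 45 per group for the pain score (2.0 against 3.5, SD 2.5, two-sided alpha 0.05, power 0.80). The normal approximation is 2 × (1.960 + 0.842)² × 2.5² / 1.5² = 43.6, so 44; the t-test calculation gives 45. The figure reproduces. No power is stated for Aim 2.

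**5. Illustration for Aim 2.** None of these inputs is in the documents:
- SD of 3 tablets over three days, in users and non-users alike
- preoperative users are a share q of patients and take g more tablets on average
- a treatment difference of 1.8 tablets in everyone (1.8 / 3 = 0.6, the effect size in the plan's 90-patient row)

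Variance = 9 + q(1 − q)g². Effect size = 1.8 / SD. Power is from the two-sided t-test with 45 per arm.

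| q | g | Variance | Ratio to 9 | SD | Effect size | Power | n per arm for 0.80 |
|---|---|---|---|---|---|---|---|
| 0 | – | 9.00 | 1.00 | 3.00 | 0.600 | 0.80 | 45 |
| 0.10 | 3 | 9.81 | 1.09 | 3.13 | 0.575 | 0.77 | 49 |
| 0.10 | 6 | 12.24 | 1.36 | 3.50 | 0.514 | 0.68 | 61 |
| 0.20 | 3 | 10.44 | 1.16 | 3.23 | 0.557 | 0.74 | 52 |
| 0.20 | 6 | 14.76 | 1.64 | 3.84 | 0.469 | 0.59 | 73 |

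Under the same assumptions, a covariate that identifies the users brings the residual variance back to 9.

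**6. Chance imbalance is not a second harm.** The difference between arms in the share of users has SD √(2q(1 − q)/45), which is 0.063 at q = 0.10. With g = 6 that shifts the mean difference by 0.38 tablets (1 SD). The unadjusted variance of the mean difference is 2 × 12.24 / 45 = 0.544. This equals 2 × 9 / 45 + 0.38² = 0.400 + 0.144. The t-test's standard error already contains the imbalance.

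**The case against.** The strongest reply has four parts.

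- **Randomisation.** Preoperative use is balanced in expectation, the standard error already reflects chance imbalance, and type I error stays nominal. This stands. A reader might infer that the Aim 2 comparison is biased; the documents do not support that.
- **Recording.** A reader might infer that carried-over opioids are counted as rescue. No text says so, and the separate rescue and other-medication items could already keep them apart. This stands as far as it goes: what remains is an ambiguity, not a stated rule.
- **Eligibility.** A reader might infer that any daily opioid user qualifies. That ignores both the 12-week limit and the chronic-pain exclusion. This also stands; the supportable claim is that some shorter-term users can be eligible.
- **Size.** Every input to the illustration is assumed. At the low end, power falls only from 0.80 to 0.77. The high end needs one patient in five to take six extra tablets, half the 12-tablet study supply, and nothing in the documents shows that use for stone pain continues at that level once the stone is treated. This stands, and it limits the priority.

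The provision for regression after observed imbalance is a weaker reply. It needs the variable to be recorded. Because it depends on seeing an imbalance, it also does not recover precision when the arms happen to be balanced.

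**Conclusion.** The point holds as a cheap improvement to a secondary outcome. Shorter-term preoperative opioid use is not clearly excluded, is not recorded as a baseline variable, and is not in the Aim 2 analysis. The consequences are possible added variance and a less clear meaning of the opioid outcome, together with an undefined boundary between study rescue and a patient's own opioid.

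The size cannot be established from the documents. The 9% to 64% rise in variance holds only under the assumed shares, SD and extra tablets, and the matching powers of 0.77 to 0.59 also need the assumed 1.8-tablet effect. It would go too far to say that the endpoint stops measuring rescue: on these same assumptions 80% to 90% of patients are not preoperative users. Nor does the point show any error in the Power Statement, whose 45 per group reproduces and concerns the pain score. Priority: minor.

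**What to change.** 1. **Baseline.** Before surgery, ask whether the patient took any opioid in the preceding 7 days and, if yes, whether daily or occasionally. The second part keeps a single tablet distinct from weeks of daily use.
2. **Analysis.** Prespecify a linear model of cumulative opioid use on arm plus preoperative opioid use, fitted whether or not imbalance is seen.
3. **Data sheet and definition.** Have the daily sheet separate study-prescribed oxycodone from any other opioid. State which intake counts as study rescue, and report both study rescue and total opioid use.

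None of this requires a change to eligibility. The cost is a short baseline question, one data-sheet field and one degree of freedom for a yes/no term (two if none, occasional and daily are kept as three levels). With 90 patients contributing, the yes/no model leaves 90 − 3 = 87 residual degrees of freedom, so the loss is negligible. Accrual is not affected.

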Previous work looked at pain scores after ureteroscopy for upper urinary tract calculi.^{10,11} From these, and an ongoing study at the Cleveland Clinic, we estimated the mean Visual Analog Scale (VAS) score in the control group when the rescue medication is used to be 3.5 with a standard deviation of 2.5. We assume patient in the experiment group (CBD oil) will have a lower pain score and the placebo group has at least 40% higher pain score before use of the rescue medication. We assume alpha (Type I error) equals to 0.05, power (1 - Type II error) 0.80 and the standard deviation of the pain score is 2.5 for each group. Using two-sided t-test, the sample size estimations under different scenarios are listed in the table below. At Mayo Clinic Arizona we perform over 700 surgical cases for stone disease each year, so patient accrual should be amenable to completion in 12 months.

Pain score in	Pain score in	Effect size	Required sample	Total sample size
treatment group	placebo group	(difference/SD)	size for each group	
2.0	3.5	0.6	45	90
2.25	3.5	0.5	64	128
2.5	3.5	0.4	100	200
2.75	3.5	0.3	176	352

Data Analysis Plan:

All the study data will be summarized by descriptive statistics. We anticipate the baseline characteristics between study groups will be comparable due to randomization. The point estimate and 95% confidence interval (CI) of the primary and secondary outcomes (pain score and USSQ scores) will be reported and compared by the two-sample t-test. If there is imbalance in the baseline characteristics between groups, we will fit a regression model to adjust for the possible confounding effect. The use of analgesic opioid medication (number of use, cumulative and per day usage) will be reported and compared by the two-sample t-test or Chi-square test. All the adverse events observed during the study period will be reported and summarized by frequency count and percentages.

References

- 3. https://www.cdc.gov/drugoverdose/data/index.html. Accessed December 17, 2019.
- 4. Nickel JC, Medical marijuana for urologic chronic pelvic pain. Can Urol Assoc J 2018;12(6Suppl3).

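### The target of 90 gives 80% power only for the largest tabulated effect (3.5 vs 2.0), not across the stated assumption of a placebo score at least 40% higher, and no scenario is named as its basis

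*Combined protocol and SAP*

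**What the plan says.** The Power Statement (under Data Analysis) starts from the control group: "we estimated the mean Visual Analog Scale (VAS) score in the control group when the rescue medication is used to be 3.5". The SD attached to that mean is 2.5. Its only numerical assumption about the treatment effect is that "the placebo group has at least 40% higher pain score before use of the rescue medication". It then fixes two-sided alpha at 0.05, "power (1 - Type II error) 0.80 and the standard deviation of the pain score is 2.5 for each group", and says that "the sample size estimations under different scenarios are listed in the table below".

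The table holds placebo at 3.5 in every row and varies the treatment mean:

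| Treatment | Placebo | Effect size | Per group | Total |
|---|---|---|---|---|
| 2.0 | 3.5 | 0.6 | 45 | 90 |
| 2.25 | 3.5 | 0.5 | 64 | 128 |
| 2.5 | 3.5 | 0.4 | 100 | 200 |
| 2.75 | 3.5 | 0.3 | 176 | 352 |

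No sentence selects a row. Subject Information gives "Target accrual: 90" without a reason. The Methods section allocates half of the patients to each arm, so 90 means 45 per group.

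**The concern.** When a plan states an effect as a lower bound and attaches 80% power to it, a reader expects that power to hold at the bound and to be higher above it. Here the bound, taken literally, coincides with a row of the protocol's own table that asks for more than twice the target. The target equals the total for the most optimistic row, and no reason is given for preferring it.

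What is at stake is how a non-significant result would be read. Someone relying on the Power Statement could take it that the trial had an 80% chance of detecting any effect of the size assumed. If that is true only near the largest tabulated effect, a null result says much less about the smaller effects that the same sentence admits.

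**Working it through.** **Inputs.** All come from the Power Statement unless noted: SD 2.5 in each group; two-sided t-test; alpha 0.05; power 0.80; placebo mean 3.5; treatment means 2.0, 2.25, 2.5 and 2.75. Equal allocation comes from Methods, and the total of 90 from Subject Information.

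**Step 1: reproduce the table.** With d = difference / 2.5, the normal approximation is n per group = 2 × (1.960 + 0.842)² / d² ≈ 15.70 / d². The exact value solves the noncentral t power equation for n.

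| Difference | d | Normal approximation, n per group | Noncentral t, n per group | Protocol |
|---|---|---|---|---|
| 1.5 | 0.6 | 44 | 44.59 → 45 | 45 |
| 1.25 | 0.5 | 63 | 63.77 → 64 | 64 |
| 1.0 | 0.4 | 99 | 99.08 → 100 | 100 |
| 0.75 | 0.3 | 175 | 175.38 → 176 | 176 |

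All four rows reproduce exactly with the t calculation.

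**Step 2: compare each row with the 40% assumption.** The placebo excess is 3.5 / treatment mean − 1:

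- 3.5 / 2.0 − 1 = 75%
- 3.5 / 2.25 − 1 = 56%
- 3.5 / 2.5 − 1 = 40%
- 3.5 / 2.75 − 1 = 27%

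Read literally, the first three rows meet the assumption, with totals of 90, 128 and 200. The floor is 3.5 / 1.4 = 2.5, which is the 200-patient row.

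**Step 3: power of the target.** With 45 per group the noncentrality is d × √(45/2) = 4.743 × d on 88 degrees of freedom.

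| Difference | Scenario | Power with 90 |
|---|---|---|
| 1.5 | 3.5 vs 2.0 | 80.4% |
| 1.25 | 3.5 vs 2.25 | 65.0% |
| 1.0 | 3.5 vs 2.5 | 46.7% |

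At the literal floor the shortfall is 80 − 46.7, or about 33 percentage points. Solving for d at 80% power with 45 per group gives 0.597, a difference of 0.597 × 2.5 = 1.49.

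**Step 4: the alternative reading, a reduction from placebo.** Difference / 3.5 gives 42.9%, 35.7%, 28.6% and 21.4% for the four rows, so only the first reaches 40%. An exact 40% reduction is 3.5 × 0.6 = 2.1, a difference of 1.4 and d = 0.56. That needs 51.03 → 52 per group, or 104 in total. With 90 patients the power is 74.8%.

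**Step 5: slack.** The 3.5 vs 2.0 row needs 44.59 per group and is rounded up to 45. With 44 analysed per group, power is 79.5%. The documents state no expected loss, so no loss-adjusted figure is given here; the 80% simply presumes that all 90 are analysed.

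**The case against.** The strongest reply is that nothing is contradicted. A lower bound of 40% admits a 75% excess, the 75% row needs 90, and 90 is the target. Only one row totals 90, so a reader can match it at once, and the same table shows openly that smaller effects need 128, 200 or 352. That stands as far as it goes: the target is compatible with the assumption. It does not follow from it, because 128 and 200 satisfy the same assumption equally well, and the power of 90 patients at those effects is never given.

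A second reply is that 40% may have been meant as a reduction from placebo. The 3.5 vs 2.0 row would then be the only qualifying row, which may well explain the 90. This is the most favourable explanation and the sponsor should say whether it is right. But the text says higher, not lower, and a reduction of exactly 40% would still need 104.

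A third is that the Data Analysis Plan already promises a point estimate and 95% confidence interval, which readers can use to judge a null result. This limits the harm but does not correct the power claim.

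Stronger readings are tempting and are not supported:

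- A reader might infer that the table is miscalculated. It is not; every row reproduces.
- A reader might infer that the trial must enrol 200. That would follow only if the sponsor meant to power at the literal floor, which the documents do not say.
- Because the 3.5 is described with rescue medication in use and the 40% contrast as before it, a reader might build a 4.9 vs 3.5 contrast. The table fixes placebo at 3.5 in every row and speaks against this.
- A reader might fold in the choice between daily maximum and average scores, or the routes by which diaries are returned. Those questions would arise whichever row was chosen and do not bear on this point.

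**Conclusion.** The point holds as an unstated basis for the target and a power claim wider than the target supports. With 90 patients the trial has 80% power for a difference of about 1.5 (1.49 by calculation), but not across effects as small as a 40% placebo excess. Power falls to 65.0% at 3.5 vs 2.25 and to 46.7% at the literal floor, 3.5 vs 2.5. Under the reduction reading the gap is much smaller: 74.8% against 80% at an exact 40% reduction.

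These figures rest on the protocol's own SD of 2.5 in both groups, placebo at 3.5, two-sided alpha 0.05, equal groups and all 90 patients analysed. Differences are in the table's own units; the Power Statement does not relate them to the 100-mm scale. The documents do not establish an arithmetic error, and they do not establish that 90 is the wrong number. This should be fixed, but it does not call the design into question.

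**What to change.** Keep the target at 90 and rewrite the Power Statement.

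1. The sponsor confirms which scenario the target rests on. The table implies 3.5 vs 2.0, but that is for the sponsor to state, with the reason for choosing it.
2. If that row is confirmed, wording along these lines would do: *The target of 90 patients (45 per group) is based on mean scores of 3.5 and 2.0 with SD 2.5, using a two-sided t-test at alpha 0.05. Power is 80% only for a difference of about 1.5, with all 90 patients analysed. Power is about 75% for a difference of 1.4, 65% for 1.25 and 47% for 1.0.*
3. Reword or remove the 40% statement so that it matches the confirmed row. If a reduction from placebo was meant, say so; the 3.5 vs 2.0 row is 42.9% lower.

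This changes text only; the sample size and the analysis stay as they are. The price is a less favourable statement, because the 80% claim is confined to the largest tabulated effect and lower power is disclosed for smaller ones.
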